8.3.7 Study pausing rules

Participant safety will be continuously monitored by the Medical Monitor, designated Safety Lead (or delegate), throughout the study. Pertinent findings and conclusions are shared with the product's SRT for review of the overall benefit-risk profile of the product. The Sponsor's governance group, VSLC will review data and the team's recommendation when any pausing/stopping rules are met. The VSLC is comprised of senior representatives from various departments, including clinical development, safety, toxicology, pharmacovigilance, epidemiology, and medical affairs. The VSLC will govern whether enrollment may be resumed/modified, a given treatment arm will be stopped, or the study stopped. (See Section 10.1.6 for more details on VSLC)

The following study pausing criteria would be applied:

- Death of a participant, regardless of investigator's assessment of causality
- Any Grade 4 event or an SAE, regardless of its severity, that is considered to be clinically significant and reasonably attributable to dosing with VH4524184 in the opinion of the investigator or the Sponsor.
- Any Grade 3 or higher AE (of the same type) in 2 or more participants, leading to the decision to withdraw from the study (by the investigator), assessed by the investigator as reasonably attributable to VH4524184.
- Any Grade 2 or higher rash with evidence of systemic involvement (e.g., fever, liver transaminase elevation and/or eosinophilia) that the investigator considers reasonably attributable to VH4524184 occurring in two or more participants.
- Any Grade 4 laboratory abnormality (of the same type) or Grade 3 laboratory abnormalities (of the same type, with the exception of an asymptomatic Grade 4 lipid abnormalities or CPK increase) that the investigator considers reasonably attributable to VH4524184, in two or more participants.
- Any participant meeting liver stopping criteria that the investigator considers reasonably attributable to VH4524184.
- Any participant meeting QTc stopping criteria that the investigator considers reasonably attributable to VH4524184.
- Clinically significant arrhythmia in two or more participants.

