8.4.7 Disease-related events and/or disease-related outcomes not qualifying as AEs or SAEs

The events or outcomes listed in the CDC Classification System for HIV-1 Infections (Section 10.7) will be recorded on the HIV-Associated Conditions eCRF page if they occur. However, these individual events or outcomes, as well as any sign, symptom, diagnosis, illness, and/or clinical laboratory abnormality that can be linked to any of these events or outcomes are not reported to VH/GSK as AEs and SAEs even though such event or outcome may meet the definition of an AE or SAE, **unless the following conditions apply:**

- The investigator determines that the event or outcome qualifies as an SAE under part 'f' of the SAE definition (Section 10.3.2), or
- The event or outcome is in the investigator's opinion of greater intensity, frequency or duration than expected for the individual participant, or
- The investigator considers that there is a reasonable possibility that the event was related to study intervention.
- Death occurring for any reason during a study, including death due to a disease-related event, will always be reported promptly, or
- Lymphomas and invasive cervical carcinomas are excluded from this exemption; they must be reported as SAEs even if they are considered to be HIV-related.
- If any of the above conditions are met then record the DRE on the SAE page rather than the HIV Associated Conditions eCRF.

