- The disease/disorder being studied or expected progression, signs, or symptoms of the disease/disorder being studied, unless more severe than expected for the participant's condition.
- Medical or surgical procedure (e.g., endoscopy, appendectomy): the condition that leads to the procedure is the AE.
- Situations in which an untoward medical occurrence did not occur (social and/or convenience admission to a hospital, admission for routine examination.).
- Anticipated day-to-day fluctuations of pre-existing disease(s) or condition(s) present or detected at the start of the study that do not worsen. Pre-existing diseases will be recorded in the medical history section of the eCRF.
- Hospitalization for elective treatment of a pre-existing condition (known or diagnosed before signing the informed consent) that did not worsen from baseline.
- DRE, typically associated with the disease under study. These events will be recorded in the participant's eCRF and will be monitored by SRT on a routine basis. However, if 1 or both of the following conditions apply, then the event should be reported promptly to VH/GSK as an SAE (see Section 8.4.8):
 - The event is, in the investigator's opinion, of greater intensity, frequency, or duration than expected for the individual participant, or
 - The investigator considers that there is a reasonable possibility that the event was related to the administration of the study intervention

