10.3.2 Definition of SAE

An SAE is defined as any untoward medical occurrence that, at any dose, meets one or more of the criteria listed:

a. Results in death

b. Is life threatening

The term 'life-threatening' in the definition of 'serious' refers to an event in which the participant was at risk of death at the time of the event. It does not refer to an event, which hypothetically might have caused death, if it were more severe.

c. Requires inpatient hospitalization or prolongation of existing hospitalization

- In general, hospitalization signifies that the participant has been admitted (usually involving at least an overnight stay) at the hospital or emergency ward for observation and/or treatment that would not have been appropriate in the physician's office or outpatient setting. Complications that occur during hospitalization are AE. If a complication prolongs hospitalization or fulfills any

other serious criteria, the event is serious. When in doubt as to whether “hospitalization” occurred or was necessary, the AE should be considered serious.

 • Hospitalization for elective treatment of a pre-existing condition that did not worsen from baseline is not considered an AE.

 d. Results in persistent or significant disability/incapacity

 • The term disability means a substantial disruption of a person’s ability to conduct normal life functions. • This definition is not intended to include experiences of relatively minor medical significance such as uncomplicated headache, nausea, vomiting, diarrhea, influenza, and accidental trauma (e.g., sprained ankle) that may interfere with or prevent everyday life functions but do not constitute a substantial disruption.

 e. Is a congenital anomaly/birth defect in the offspring of a study participant

 f. Abnormal pregnancy outcomes (e.g., spontaneous abortion, fetal death, stillbirth, congenital anomalies, ectopic pregnancy)

 g. Is a suspected transmission of any infectious agent via an authorized medicinal product

 h. Other situations:

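### Sections 8.4.7 and 10.3.1 make a disease-related event an SAE when it is judged related or worse than expected, without the seriousness criterion that 10.3.2 requires

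*Protocol*

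**What the plan says.** Protocol 8.4.7 takes the events and outcomes in the CDC classification (10.7), with any linked sign, symptom, diagnosis or laboratory abnormality, out of AE and SAE reporting. It does so "even though such event or outcome may meet the definition of an AE or SAE". Five conditions lift the exemption. Two matter here: that the event is, in the investigator's opinion, "of greater intensity, frequency or duration than expected for the individual participant", or that "there is a reasonable possibility that the event was related to study intervention". The section closes with the recording rule: "If any of the above conditions are met then record the DRE on the SAE page rather than the HIV Associated Conditions eCRF".

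Protocol 10.3.1 gives the same two conditions and says that if one or both apply, "then the event should be reported promptly to VH/GSK as an SAE".

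Protocol 10.3.2 defines the term differently: "An SAE is defined as any untoward medical occurrence that, at any dose, meets one or more of the criteria listed". The note in 10.3.6.2 also ties the word serious to those listed outcomes.

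Two rules use SAE status. The pausing list in 8.3.7 includes "Any Grade 4 event or an SAE, regardless of its severity, that is considered to be clinically significant and reasonably attributable to dosing", and the individual stopping list in 7.1 has a parallel item. SAP 4.3.2.1 plans separate displays for SAEs and for drug-related SAEs.

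**The concern.** Relatedness and intensity are not seriousness. Under 10.3.2 a mild, related event managed without admission is a non-serious AE. Under 8.4.7 and 10.3.1, the same event, if it falls within the disease-related list, is an SAE. A site following one section breaches the other, and two sites could classify the same event differently in good faith.

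The stake is the reading of the safety results. SAEs and drug-related SAEs are among the first rows looked at in a small early study, and the groups are small enough for one event to change them visibly. SAE status is also one of the elements of the criteria in 7.1 and 8.3.7.

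**Working it through.** The plan states no figure on this point, so the check is a comparison of sections, followed by simple proportions for scale.

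**1. Does either condition test seriousness?** The lead-in to 8.4.7 covers events that meet the AE definition as well as the SAE definition, so non-serious events are in scope. The conditions are alternatives: any one is enough. The other three concern an event that qualifies as an SAE under part f of 10.3.2, death, and lymphoma or invasive cervical carcinoma. These largely describe events that 10.3.2 would make serious anyway. (Part f of 10.3.2 is abnormal pregnancy outcomes and the medical-judgement item is under h, so that cross-reference also needs checking.) The two conditions at issue carry no seriousness element, and no route leads to the AE page.

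**2. Does the SAE definition absorb them?** No. Where 10.3.2 wants an event type always treated as an SAE, it lists it, as for possible Hy's Law cases under h. Related or worse-than-expected disease events are not listed. Section 10.3.6.2 adds that an asymptomatic Grade 4 laboratory value is not automatically an SAE. Section 8.3.4 treats disease-associated laboratory findings that are more severe than expected as AEs or SAEs according to which definition they meet. The same kind of finding is therefore classified by definition in one place and by form in another.

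**3. Follow a non-serious disease-related event through the plan.**

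| Step | Judged related | Judged only worse than expected |
|---|---|---|
| Recording (8.4.7) | SAE page | SAE page |
| SAE display (SAP 4.3.2.1)* | counted | counted |
| Drug-related SAE display* | counted | not counted |
| SAE-based criteria (7.1, 8.3.7) | met only if also judged clinically significant | not met, as there is no attribution to the drug |

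*If the displays take SAEs from the SAE page.

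**4. What does the label add to the criteria?** The 7.1 list is permissive and already includes related AEs of Grade 3 or higher without seriousness, so the addition there is mainly related Grade 1 or 2 events. In 8.3.7 the same item already covers attributable Grade 4 events, so the addition is in Grades 1 to 3. Apart from the liver and QTc criteria, related events in that range otherwise count under items that need two or more participants.

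**5. Scale.** Protocol 4.1 gives 6 active participants per cohort and 3 cohorts in Part 1, so 3 × 6 = 18 active participants.

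- One event in a dose group: 1/6 = 16.7%, against 0.
- One event among Part 1 active participants: 1/18 = 5.6%, against 0.

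SAP 4.1.1 reports each active dose separately, so the first is the figure a table would show.

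**The case against.** The strongest defence is that this is deliberate, conservative escalation. It appears in two places, over-reporting errs toward participant protection, and the study is descriptive. That explains why the sponsor would want early sight of such events. It does not explain the label: prompt notification can be required without calling a non-serious event an SAE.

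The second defence is rarity, and it stands. Active CDC Stage 3 disease is excluded apart from cutaneous Kaposi's sarcoma not needing systemic therapy, screening CD4 must be at least 200, ART starts on Day 10 and follow-up ends at Day 38. Many illnesses in 10.7 would meet a seriousness criterion if they occurred.

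The third also stands. SAP 4.3.2.1 does not say whether its displays use the eCRF page or a seriousness flag. It leaves them to the Output and Programming Specifications, which are not among the documents.

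A reader might also infer more than the text supports:

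- *Every such event enters the stopping and pausing criteria.* It does not. Both criteria also require clinical significance and attribution to the drug.
- *A CD4 count drifting below 200 becomes an SAE.* Whether a staging threshold is an event or outcome is arguable, and the investigator would still have to judge the fall related or worse than expected.
- *Sections 8.4.7 and 10.3.1 differ materially because one lists five conditions and the other two.* The three missing from 10.3.1 mostly describe events already serious under 10.3.2.
- *Leaving the HIV Associated Conditions page damages an analysis.* SAP 6.1.2 makes those data available only at participant level, and no endpoint uses them.

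**Conclusion.** The conflict is real. Sections 8.4.7 and 10.3.1 assign SAE status on relatedness or intensity, while 10.3.2 and 10.3.6.2 assign it on listed outcomes. This is a stated rule that misclassifies an event when followed, not a missing detail.

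The consequence is narrow. A non-serious event judged related is recorded as an SAE. It is displayed as a drug-related SAE if the tables follow the page, and it can meet the SAE-based criteria only if also judged clinically significant. An event judged only worse than expected adds to the SAE count alone. One event moves a dose group from 0 to 16.7%, or Part 1 active participants from 0 to 5.6%. These figures assume that all planned active participants are dosed and that the displays take SAEs from the SAE page.

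The expected number of affected events, perhaps none or one, is a judgement from the entry criteria and short follow-up; the documents give no rate. The primary analysis is not affected, and nothing here shows that the stopping or pausing rules are wrong.

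**What to change.** 1. Reconcile protocol 8.4.7, 10.3.1, 10.3.2 and 10.3.6.2. In 8.4.7 and 10.3.1, state that an event that loses the exemption goes to the SAE page if it meets at least one criterion in 10.3.2, and otherwise to the AE page. Check the part f cross-reference in the same edit.
2. If the sponsor wants early sight of related or worse-than-expected disease events, keep prompt notification as a separate requirement, independent of the SAE label.
3. In SAP 4.3.2.1, state that SAEs are identified by the 10.3.2 criteria and not by the eCRF page.
4. Optionally, complete the HIV Associated Conditions page in every case.

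The stopping and pausing rules need no change for this point. The cost is minor protocol and SAP wording plus eCRF completion guidance. The gain is correspondingly modest, since few events are likely to be affected.

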8.4.9 Participant card

The investigator (or designee) must provide the participant/participant's LAR(s) with a "participant card" containing information about the clinical study. The participant/participant's LAR(s) must be instructed to always keep the participant card in their possession for the duration of the study. In an emergency, this card serves to inform the responsible attending physician/LAR/caregiver/family member that the participant is in a clinical study and that relevant information may be obtained by contacting the investigator(s) or their back up.

8.5 Pharmacokinetics

- Intensive and single PK sampling is pre-specified as per the SoA (Section 1.3).

CCI

- Otherwise on single PK draw days CCI a single PK sample will be drawn in conjunction with the study visit and as close to an every 24-hour post last dose cycle as possible.
- Collected PK samples may not be analyzed if concentrations below the limit of quantification were previously achieved or if the participant was assigned to placebo.
- Refer to Table 7 for the permissible windows CCI, dosing and PK draws for intensive PK days.

Table 7 **Intensive Pharmacokinetic Sampling** **CCI**

	Time of Event	Window	Time Relative to Dosing Hour:Minute
Dosing Day	CCI [REDACTED]	Not applicable	CCI [REDACTED]
	Pre-dose PK collection	Not applicable	Collect pre-dose sample prior to dosing. There is allowance to collect the sample earlier and up to 90 minutes prior to dosing
	Administer study treatment and start the clock for subsequent blood draws.	Not applicable	00:00
	CCI [REDACTED]		

- Instructions for the collection and handling of biological samples will be provided by the sponsor and central laboratory.
 - Blood samples of approximately 2 mL will be collected and processed to plasma for measurement of plasma concentrations of study intervention.
 - The actual date and time (24-hour clock time) of each sample will be recorded.
 - Samples to be stored in an upright position at -70°C or colder until shipment to the test laboratory. Refer to the List of Clinical Laboratories and Key Vendors document for laboratory names and addresses of the clinical laboratories used in this study.
- A maximum of 2 mL samples may be collected at additional timepoints during the study if warranted and agreed upon between the Investigator and the sponsor. The timing of sampling may be altered during the study based on newly available data (e.g., to obtain data closer to the time of peak plasma concentrations) to ensure appropriate monitoring.
- Plasma samples will be used to evaluate the PK concentrations of VH4524184 and may also be used to evaluate safety or efficacy aspects related to concerns arising during or after the study.
- Intervention concentration information that would unblind the study will not be reported to investigative sites or blinded personnel until the study has been unblinded.

8.6 Pharmacodynamics

See Section 8.2 and Section 8.5 for relevant efficacy and PK assessments.

8.7 Genetics

Genetics are not evaluated in this study.

8.8 Biomarkers

Plasma samples for exploratory resistance testing will be collected according to the schedule described in Section 1.3 and as detailed in the Laboratory Manual.

Resistance results will not be available in time to inform the treatment management of participants during the study. Samples from Day 1 (pre-dose) and Day 10 will be batch tested for viral genotypic and phenotypic on treatment changes and/or resistance to the CCI using the Monogram Biosciences Inc. based assays. Plasma from additional timepoints may be assayed if needed.

Additional blood samples may be drawn for local genotypic/phenotypic analysis, according to local guidelines. These tests are optional and will be conducted in accordance with local guidelines for the management of HIV-1 infection and, if available, may be used to guide the choice of standard of care ART. Locally obtained genotypic/phenotypic results will be retained in the participant's medical record at the site and will not be transferred to VH/GSK.

VH/GSK may store samples for up to 20 years after the end of the study to achieve study objectives. Additionally, with participants' consent, samples may be used for further research by VH/GSK or others such as universities or other companies to contribute to the understanding of HIV-1 or other diseases, the development of related or new treatments, or research methods.

8.9 Immunogenicity assessments

Immunogenicity is not evaluated in this study.

8.10 Health economics or medical resource utilization and health economics

Health economics OR Medical resource utilization and health economics parameters are not evaluated in this study.

9 STATISTICAL CONSIDERATIONS

The statistical analysis plan (SAP) will be finalized prior to database lock and it will include a more technical and detailed description of the statistical analyses described in this section. This section is a summary of the planned statistical analyses of the most important endpoints including primary and key secondary endpoints. If methods in the SAP differ from the methods described in the protocol, the SAP will be followed.

9.1 Statistical hypotheses

The primary objective will be addressed using an estimation approach (descriptive statistics) with no hypothesis testing. The primary treatment effect to be estimated is the maximum change from baseline in plasma HIV-1 RNA over the monotherapy period.

9.2 Analysis sets

Analysis Set	Definition / Criteria	Analyses Evaluated
Screened	
 All participants who were screened for eligibility. 	
 Study Population
Randomized	
 All participants who were randomly assigned to study intervention in the study. The screened, enrolled and randomized populations must be nested, i.e. the enrolled population must be a subset of the screened population, the randomized population must be a subset of the enrolled population. 	
 Study Population
Safety	
 All participants who received at least 1 partial or full dose of study intervention. Participants will be analyzed according to the study intervention they actually received. 	
 Safety
Full Analysis Set (FAS)	
 All randomized participants who received at least 1 full dose of study intervention. Data will be reported according to the randomized study intervention. 	
 Efficacy
Per-protocol (PP)	
 All participants in the FAS for whom there were no major protocol deviations that impact the primary analyses. Data will be reported according to the study intervention actually received. Specific details of major protocol deviations that would exclude participants from the PP analysis set will be provided in the SAP. 	
 Efficacy

Analysis Set	Definition / Criteria	Analyses Evaluated
Pharmacokinetic (PK)	
 • All participants in the Safety analysis set who had at least 1 non-missing PK assessment (Non-quantifiable [NQ] values will be considered as non-missing values). • Data will be reported according to the actual study intervention. 	
 • PK

9.3 Statistical analyses

9.3.1 General considerations/definitions

Data will be summarized by study intervention and dose level, unless otherwise specified.

Data will be summarized either by visit or separately for the monotherapy period and overall (i.e., monotherapy period plus SOC period), as appropriate for each endpoint, unless otherwise specified.

For all endpoints, the baseline value will be the latest pre-dose assessment with a non-missing value, including those from unscheduled visits.

Continuous and categorical variables will be summarized using the following descriptive statistics, unless otherwise specified:

- Continuous data: n (number of participants used for the summary), arithmetic mean, SD, median, interquartile range, minimum and maximum. For PK data, geometric mean, SD of log-transformed data and geometric %CVb may also be used.
- Categorical data: number and percentage of participants

9.3.2 Primary endpoint/estimand analysis

See Section 3.1 for definition of primary endpoint/estimand.

9.3.2.1 Definition of endpoint/estimands

Plasma HIV-1 RNA values will be used for the primary efficacy analysis. Change from baseline will be calculated for each participant at each assessment time point during the monotherapy period in the original and \log_{10} scales. Maximum change from baseline during the monotherapy period will be calculated for each participant from the set of available change from baseline values at each assessment time point in the original and \log_{10} scales. The \log_{10} transformation is used to allow for direct comparisons with data from other compounds publicly available in the same scale, and hence aid in interpretation.

